### **TB Prophylaxis**

If the subject has evidence of latent TB infection (newly positive TB test and the subject has a CXR not suggestive of active TB), prophylactic treatment must be initiated (per local guidelines). The prophylaxis needs to be completed.

**Of note: Rifampicin or rifapentine is not allowed for TB prophylaxis**

### **QuantiFERON-TB Gold Test**

QuantiFERON-TB Gold test will be performed at visits specified in [Table 2](#). The analyses will be performed by a certified laboratory.

**OR**

### **TB Skin Test**

A PPD skin test (alternatively, also known as a TB Skin Test) will be performed as specified in [Table 2](#) according to standard clinical practice. The TB Skin Test should be read by a licensed healthcare professional between 48 and 72 hours after administration. A subject who does not return within 72 hours will need to be rescheduled for another skin test. The reaction will be measured in millimeters (mm) of induration and induration equal to or greater than 5 mm for RA subjects is considered a positive reaction. The absence of induration will be recorded as "0 mm" not "negative."

### **Chest X-Ray (CXR)**

A CXR (posterior-anterior and lateral views) is required at the visits indicated in [Table 2](#) for those subjects with new TB risk factors per the latent TB risk factor questionnaire ([Appendix L](#)), or for those subjects living in areas endemic for TB or for those subjects with a newly positive PPD or QuantiFERON-TB Gold. Subjects can have a CXR any time during the study as warranted based on the opinion of the Investigator.

A radiologist must perform an assessment of the CXR. The Principal Investigator will indicate the clinical significance of any findings and will sign and date the report. In the assessment of the CXR, the Principal Investigator or their delegate must indicate the presence or absence of (1) calcified granulomas, (2) pleural scarring/thickening, and (3) signs of active TB.

Due to a state of emergency or pandemic situation like COVID-19, subject visits may be conducted via phone or video conference. In these situations, if a visit requires

completion of a CXR, the CXR will be performed at the next earliest feasible visit, unless the Investigator has determined, based on clinical judgement, that a CXR is required to ensure that it is safe to continue study drug administration. In this case, CXR should be performed as soon as restrictions allow at the study site or local hospital/facility.

### **12-Lead Electrocardiogram (ECG)**

An ECG will be performed for all subjects at Weeks 0, 48, 96 and every 48 weeks afterwards (Wk 132, Wk 180, Wk 228 and Wk 276), until the end of the study or as clinically indicated during the study. An ECG may be administered at any time during the study based on the opinion of the Investigator.

Due to a state of emergency or pandemic situation like COVID-19, subject visits may be conducted via phone or video conference. In these situations, if a visit requires completion of an ECG, the ECG will be performed at the next earliest feasible visit, unless the Investigator has determined, based on clinical judgement, that an ECG is required to ensure that it is safe to continue study drug administration. In this case, the ECG should be performed as soon as restrictions allow at the study site or local hospital/facility.

### **hsCRP**

Blood samples for high-sensitivity C-reactive protein (hsCRP) will be obtained at the time points specified in [Table 2](#).

### **Pharmacokinetic (PK)**

Blood collection will be performed at the scheduled study visits as specified in [Table 2](#).

### **Clinical Laboratory Tests**

Samples will be obtained at minimum for the clinical laboratory tests outlined in [Table 3](#). A certified central laboratory will be utilized to process and provide results for the clinical

laboratory tests. All abnormal laboratory tests that are considered clinically significant by the investigator will be followed to a satisfactory resolution.

The central laboratory chosen for this study will provide instructions regarding the collection, processing and shipping of these samples.

The fasting status will be recorded in the study source documentation.

If travel restrictions or other changes in local regulations due to state of emergency or pandemic situation like COVID-19 prevent the subject from having blood drawn for laboratory testing at the study site, it is possible for the Investigator to arrange for subjects to have laboratory work done at a local lab, hospital, or other facility to ensure the safety assessments are conducted per protocol. Local lab results should be obtained along with reference ranges and kept within the subjects' source documentation. Local lab results should be reviewed by the investigator or designee as soon as possible and documented in the eCRF.

If laboratory samples cannot be obtained, study drug administration may be continued provided labs have been obtained within the prior 3 months, the investigator has reviewed the laboratory results and confirmed and discussed with the subject that there is no safety concern for the subject to continue use of the study drug in the absence of current lab results. The subject should be scheduled for laboratory draws as soon as feasible and no later than the next scheduled visit in order to continue the study drug administration.

If laboratory results are not available within the prior 3 months/two consecutive 12-week intervals, study drug dispensation is not allowed until the required laboratory tests are completed to ensure the safety assessments are conducted per protocol.

Blood and samples will be obtained for the laboratory tests as specified in [Table 2](#). Blood draws should be performed after all clinical assessments and questionnaires (HAQ-DI, Patient's Assessment of Pain, FACIT, etc.), and vital sign determinations are obtained and before study drug administration during a visit.

Urine samples will be obtained for urinalysis testing as specified in [Table 3](#). The central laboratory will be responsible for performing a macroscopic urinalysis (urine dipstick) on the collected urine specimens. Specified abnormal macroscopic urinalyses defined as protein, ketones or blood greater than negative, or glucose greater than normal will be followed up with a microscopic analysis at the central laboratory.

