### **Treatment Period**

The treatment period for OLE can begin immediately after or up to 30 days following the Last Visit (Week 12) of Study M13-550 or Study M13-537 RCT and will continue for approximately 312 weeks in OLE. At Last Visit (Week 12) or up to 30 days following the Last Visit (Week 12) of Study M13-550 or Study M13-537, subjects who meet all the inclusion criteria and none of the exclusion criteria described in Section 5.2.1 and Section 5.2.2 will be enrolled into the study. Subjects will visit the study site at Weeks 6, 12, 18 (Optional), 24, 36, 48, 60, 72, 84, 96 and every 12 weeks thereafter until the end of the study or if they terminate early from the study. A  $\pm$  7-day window is permitted around scheduled study visits. The last dose of study drug is taken the evening prior to the final visit.

Subjects may discontinue study drug treatment at any time during study participation. Subjects that end study participation early will have a Premature Discontinuation Visit and complete the procedures outlined for Premature Discontinuation Visit in Table 2 as soon as possible, preferably within 2 weeks of study drug discontinuation and preferably prior to initiation of another therapy.

Starting with Amendment 5, subjects who are receiving 30 mg QD open-label upadacitinib will have the option to decrease to the 15 mg QD dose based on investigator's discretion.

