## **Protocol Modifications due to State of Emergency or Pandemic like COVID-19**

Study visits may be impacted by a pandemic situation (including the COVID-19 pandemic) or any state of emergency. If visits cannot be conducted onsite due to travel restrictions or other pandemic-related reasons, virtual visits, visits at alternative locations, or changes in the visit frequency and timing of study procedures, among others may be performed. Additional details are provided in the subsequent sections. Every effort should be made to ensure the safety of subjects and site staff, while maintaining the integrity of the study.

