### **Study Medication Dispensing, Dosing and Compliance**

Study drug and Dosing Diary ([Appendix K](#)) will be dispensed to subjects beginning at the Baseline (Week 0) in this OLE study and at all scheduled and unscheduled study visits as specified in [Table 2](#). No study medication will be dispensed at Final Visit. First dose of study medication will occur after all other Baseline (Week 0) procedures are completed. At each visit, the site personnel will review and copy the Dosing Diary and review the drug bottles to verify compliance. The dosing records, returned unused bottles and empty used bottles will be reviewed and verified for compliance at each visit by the research personnel at the study center. All relevant dosing information will be entered into the eCRF at each visit, as applicable.

(Refer to Section [5.5](#) for additional information).

Study drug may be shipped from the study site directly to the study subject's home due to study modifications related to a state of emergency or pandemic situation like COVID-19 if all the following criteria are met:

- Direct-to-patient (DTP) shipment of study drug is allowed by local regulations and the relevant ethics committee
- Subject agrees to have the study drug shipped directly to their home
- Shipments may also include other study supplies (e.g., drug dosing diaries, in-home urine pregnancy test kits). Instructions will be provided by AbbVie as to how a study site can initiate a DTP shipment using Marken, a global vendor selected by AbbVie to provide this service when necessary. Shipments of study drugs from the study site to a subject's home will be appropriately temperature controlled (qualified shipper or temperature monitoring) within the labeled storage conditions. Signature is required upon delivery; due to COVID-19 related social distancing, this may be provided by the courier after delivery. Documentation of the shipment is to be retained by the clinical site.
- AbbVie will not receive subject identifying information related to these shipments, as the site will work directly with the courier.

The study site is responsible for meeting IRB/IEC reporting requirements related to DTP shipments of study drug, and for obtaining consent to provide delivery information to the courier and documenting this consent in source documents.

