### **8.2 Determination of Sample Size**

It is anticipated that up to 500 subjects will be enrolled in this OLE study.

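### The pandemic laboratory rule joins two unequal periods, 3 months and 24 weeks, into one limit on dispensing, and the protocol does not say which governs

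*Protocol*

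**What the plan says.** Two consecutive paragraphs of Protocol 5.3.1.1, Clinical Laboratory Tests, cover subjects whose samples cannot be obtained in a pandemic or state of emergency.

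- **Administration.** Without current samples, "study drug administration may be continued provided labs have been obtained within the prior 3 months". The investigator must also have reviewed those results and confirmed with the subject that there is no safety concern. A deadline for the make-up draw follows: "The subject should be scheduled for laboratory draws as soon as feasible and no later than the next scheduled visit".
- **Dispensation.** "If laboratory results are not available within the prior 3 months/two consecutive 12-week intervals, study drug dispensation is not allowed" until the required tests are completed.

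The timing context is elsewhere. Protocol 5.1, Treatment Period, has visits at Weeks "84, 96 and every 12 weeks thereafter until the end of the study or if they terminate early from the study", and a plus or minus "7-day window is permitted around scheduled study visits". The emergency provisions of Protocol 5.1 add that "changes in the visit frequency and timing of study procedures, among others may be performed", with no stated upper limit. Supply need not coincide with an on-time clinic visit. Table 2 includes dispensing at unscheduled visits, and the dispensing subsection of 5.3.1.1 says: "Study drug may be shipped from the study site directly to the study subject's home due to study modifications related to a state of emergency".

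**The concern.** The dispensation sentence is written as one threshold but contains two. One 12-week interval is close to 3 months; two are not. A site coordinator with a subject whose last results are, say, 110 days old gets a bar from one half of the phrase and no bar from the other.

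The thresholds in Table 5 for interrupting or stopping drug (hemoglobin, neutrophils, lymphocytes, white cells, platelets, transaminases, creatinine, CPK) can act only if there are results. The dispensation sentence is one of two provisions that apply when there are none. If sites read it differently, subjects in the same position are supplied at one site and not at another, and monitors cannot consistently classify the outcome as a deviation under Protocol 7.0. Withholding has consequences of its own: under Protocol 5.5.3 an interruption beyond 30 days leads to a decision on restart or discontinuation.

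**Working it through.** The plan gives no derived figure to reproduce. The check is calendar arithmetic on the two stated periods.

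**Inputs.** 3 months and two 12-week intervals (Protocol 5.3.1.1, Clinical Laboratory Tests); 12-week visit spacing and the 7-day window on either side (Protocol 5.1, Treatment Period).

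**Length of the two periods.**
- 3 months, counted back from every date over two years from December 2020: 89 to 92 days, mean 91.3.
- Two 12-week intervals: 2 × 12 × 7 = 168 days.
- Difference: 168 − 92 = 76 to 168 − 89 = 79 days. Ratio: 168 / 91.3 = 1.84.

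**Effect by age of the last results at the time of a dispensing decision.**

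| Age of last results | 3-month limit | 24-week limit |
|---|---|---|
| up to 89 days | not barred | not barred |
| 90 to 92 days | depends on the calendar months | not barred |
| 93 to 168 days | barred | not barred |
| over 168 days | barred | barred |

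**Whether the gap can be reached.**
- Nominal single missed draw: 12 × 7 = 84 days, inside both limits.
- In-window visits: 84 − 14 = 70 to 84 + 14 = 98 days apart.
- Reaching 93 days within the windows needs 93 − 84 = 9 days of combined shift. One visit can supply at most 7, so the earlier visit must be at least 2 days early and the later one at least 2 days late.
- Delayed visits, unscheduled dispensing and home shipments can fall anywhere in the 93 to 168 day band.

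**What the slash could mean.**
- *Either lapse bars supply*: 3 months always governs and the second phrase does nothing.
- *Both must lapse*: 168 days governs and the first phrase does nothing.
- *That is*: the two periods are offered as equal, which they are not.
- *Two consecutive missed 12-week draws*: agrees with 3 months on an exactly nominal schedule (84 days not barred, 168 days barred), but differs for a first missed draw at 93 to 98 days and for delayed visits or off-schedule shipments.

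**Whether the preceding paragraph decides it.** Its 3-month condition favors the shorter period. Its make-up deadline does not: if the day-84 draw is missed, the next scheduled visit is at 84 + 84 = 168 days, which is the longer period. Either reading can be defended from the same paragraph.

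**The case against.** The strongest reply is that the dispensation sentence only prohibits; it grants nothing. If either lapse bars supply, 3 months always governs and no subject gets two answers. The paragraph on administration also ties continued dosing to results within 3 months, with investigator review and a discussion with the subject, so a site that read the dispensing rule as 24 weeks would still have no clear permission to dose throughout that time. The scope is narrow as well: the rule applies only when samples cannot be obtained, and the protocol offers local laboratories (5.3.1 and Clinical Laboratory Tests) and, where permitted, home blood collection (Optional Home Healthcare Service).

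Much of this stands. It limits how often the ambiguity matters and how far a misreading could go. It does not remove the ambiguity, because no section states the *either lapse* reading, and the make-up deadline in the administration paragraph points toward 168 days.

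A reader might infer more than the documents support:
- *The same subject is at once barred and allowed.* That depends on how the slash is read. The text supports only that sites may read it differently.
- *Many subjects pass 3 months after one missed draw.* The nominal age is 84 days, and 98 days is the extreme of the windows. No distribution of visit timing is given.
- *Exposure and interruption data are materially distorted.* SAP 7.0 tabulates COVID-19 logistical restrictions as a reason for discontinuation, but nothing in either document sizes an effect from this rule.

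**Conclusion.** The point holds as an internal inconsistency in a safety threshold. The two periods differ by 76 to 79 days, and sites can reach opposite dispensing decisions when the last results are about 93 to 168 days old. This rests on reading 3 months as calendar months and two 12-week intervals as 168 days inclusive, and on the slash being undefined, which is how the text stands. The affected cases are limited to those listed under the working, and to subjects for whom local or home collection also failed; their number cannot be estimated from the documents. The consequence lies in safety conduct and deviation classification. No efficacy estimate depends on it.

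**What to change.** The sponsor should reconcile the two periods in the dispensation sentence with each other, and with both the 3-month condition and the make-up deadline in the preceding paragraph, so that dispensation and administration follow one unambiguous limit. This review takes no view on which limit is right or on when the clock should start. The cost is a clarifying letter to sites or a line in the next amendment, with no added procedures.

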**Table 3. Clinical Laboratory Tests**

Hematology	Clinical Chemistry	Urinalysis a	Other Laboratory Tests
Hematocrit	Blood Urea Nitrogen (BUN)	Specific gravity	Serum pregnancy Test (Human Chorionic Gonadotropin [HCG]) b
Hemoglobin	Creatinine	Ketones	
Red Blood Cell (RBC) count	Total bilirubin	pH	
White Blood Cell (WBC) count	Serum glutamic-pyruvic transaminase (SGPT/ALT)	Protein	High sensitivity C-reactive protein (hs-CRP)
Neutrophils	Serum glutamic-oxaloacetic transaminase (SGOT/AST)	Blood	FSH c
Bands	Alkaline phosphatase	Glucose	
Lymphocytes	Creatinine Phospho-Kinase (CPK)	Urobilinogen	
Monocytes	Sodium	Bilirubin	
Basophils	Potassium	Microscopic examination, if needed	
Eosinophils	Chloride		
Reticulocytes	Bicarbonate		
Platelet count (estimate not acceptable)	Calcium		
	Inorganic phosphorus		
	Uric acid		
	Cholesterol		
	LDL cholesterol		
	HDL cholesterol		
	Total protein		
	Glucose		
	Triglycerides		
	Albumin		
	INR (reflex only) d		

- a. A dipstick urinalysis will be completed by the central laboratory at all required visits. A microscopic analysis will be performed in the event the dipstick results show protein, ketones or blood greater than negative.
- b. Urine pregnancy test will be done at all scheduled clinic visits and at home between visits. Serum pregnancy test will be done if urine test is positive. Note that pregnancy tests are being performed only for women of childbearing potential.
- c. FSH will be done to confirm post-menopausal status if age of the female is less than 55 years with no menses for 12 or more months without an alternative medical cause AND an FSH level > 40 IU/L.
- d. INR will only be measured with a separate blood sample at repeat testing if ALT and/or AST > 3 × ULN.

For any laboratory test value outside the reference range that the investigator considers to be clinically significant:

- The investigator will repeat the test to verify the out-of-range value.
- The investigator will follow the out-of-range (Clinically Significant) value(s) to a satisfactory clinical resolution.

A laboratory test value(s) that requires a subject to be discontinued from the study or requires a subject to receive treatment will be recorded as an adverse event.

### **Concomitant Medication**

All concomitant medications and treatments are to be recorded in the appropriate eCRF as outlined in Section [5.2.3](#).

### **Enrollment and Assignment of Subject Numbers**

Subjects who meet the inclusion criteria and do not meet any of the exclusion criteria will keep the same subject number that they were assigned in Study M13-550 or Study M13-537.

### **Study Medication Dispensing, Dosing and Compliance**

Study drug and Dosing Diary ([Appendix K](#)) will be dispensed to subjects beginning at the Baseline (Week 0) in this OLE study and at all scheduled and unscheduled study visits as specified in [Table 2](#). No study medication will be dispensed at Final Visit. First dose of study medication will occur after all other Baseline (Week 0) procedures are completed. At each visit, the site personnel will review and copy the Dosing Diary and review the drug bottles to verify compliance. The dosing records, returned unused bottles and empty used bottles will be reviewed and verified for compliance at each visit by the research personnel at the study center. All relevant dosing information will be entered into the eCRF at each visit, as applicable.

(Refer to Section [5.5](#) for additional information).

Study drug may be shipped from the study site directly to the study subject's home due to study modifications related to a state of emergency or pandemic situation like COVID-19 if all the following criteria are met:

- Direct-to-patient (DTP) shipment of study drug is allowed by local regulations and the relevant ethics committee
- Subject agrees to have the study drug shipped directly to their home
- Shipments may also include other study supplies (e.g., drug dosing diaries, in-home urine pregnancy test kits). Instructions will be provided by AbbVie as to how a study site can initiate a DTP shipment using Marken, a global vendor selected by AbbVie to provide this service when necessary. Shipments of study drugs from the study site to a subject's home will be appropriately temperature controlled (qualified shipper or temperature monitoring) within the labeled storage conditions. Signature is required upon delivery; due to COVID-19 related social distancing, this may be provided by the courier after delivery. Documentation of the shipment is to be retained by the clinical site.
- AbbVie will not receive subject identifying information related to these shipments, as the site will work directly with the courier.

The study site is responsible for meeting IRB/IEC reporting requirements related to DTP shipments of study drug, and for obtaining consent to provide delivery information to the courier and documenting this consent in source documents.

**Optional Home Healthcare Service Due to State of Emergency or Pandemic Situation like COVID-19**

Subjects may be offered the option of home healthcare visits provided by a study nurse or third-party vendor. Study procedures conducted in the home setting may include vital signs and body weight, physical exam, blood and urine samples collection, urine pregnancy test, adverse event and concomitant therapy assessment including compliance to contraception requirements if applicable, latent TB risk assessment form, review of subject dosing diary, TJC and SJC performed by the same independent joint assessor, if possible, to minimize variability.

This option can only be offered in countries and sites that comply with local regulatory and IRB/IEC requirements for homecare. Any pre-requisite submissions or notifications to the site IRB/IEC and local competent health authority should be made, and approvals must be obtained prior to implementation.

The investigator should be available via phone call if a consultation is necessary.

It is recommended that medical personnel entering a subject's home adhere to local health regulations during the COVID-19 pandemic, such as the use of Personal Protective Equipment (PPE), as required.

If the home visits will not be performed by site personnel, the site may be responsible for selecting a vendor, contracting with a vendor, and for ensuring continued compliance with the terms of the Clinical Study Agreement.

Individuals performing home visits need to be added to the delegation log.

